9.6 Participant information

Written, informed consent will be obtained from all participants prior to entry into the study. The study investigator /study personnel will contact all interested patients by phone and provide information about the study. If the patient is interested in participating in the study, the study investigator/study personnel will send the written patient information (appendix 1) and the leaflet *"Forsøgspersoners rettigheder i et sundhedsvidenskabeligt forskningsprojekt"* (appendix 2) by mail or e-mail. If the patient is still interested in study participation after having read the written patient information, the study investigator /study personnel will schedule a personal meeting with the patient, offering the possibility of bringing a confidant. At the personal meeting the study objectives, significance, content and requirements including risks and implications of the study and principles for randomization with allocation to either one of two interventions or a control group will be orally explained.

In particular the patient will be informed about the following:

- The possibility of withdrawing from the study at any time without losing any patient-related benefits
- How personal and health-related data will be collected and used during the study
- That all personal and health-related data will be anonymized

The patient will be given time to discuss any questions and will be informed that he/she has at least 24 hours to decide on participation in the study. If the patient decides to participate in the study right away, the patient and the study investigator/study personnel will sign the written informed consent, and the investigator/study personnel will perform a screening to assess if the patient is eligible for inclusion in the study (see section 9.7 for screening procedure). Patient eligible for inclusion in the study investigator/study personnel. Patient needs more time to decide if he/she wants to participate in the study, the study personnel will contact the patient again within the next week. If the patient decides to participate in the study after having had time for reflection, the patient will be invited to a first visit (V1) with the purpose of screening for study eligibility, collection of baseline measurements and randomization. The patients are informed that written informed consent will be obtained prior to commencement of any study related procedures.

9.7 Screening procedure and informed consent

The study investigator/study personnel must receive a written signed consent (see appendix 4) from the patient before performing a screening. The signed consent form must also be signed by the investigator or study personnel who have been delegated the task according to the delegation log, and a copy of the signed consent must be handed over to the participant together with a copy of the patient information sheet before performing the screening. The original written signed consent will be retained by the study investigator.

In addition, the patient will be asked to sign an independent written signed consent for donation of biologic material to a biobank for future research (see appendix 5). Rejection of donation of samples to the biobank, will not affect participation in the study.

The investigator/study personnel will perform a screening to assess if the patient is eligible for inclusion in the study based on the inclusion and exclusion criteria listed in section 9.5.1 and 9.5.2. This includes having a non-fasting blood sample collected for assessment of HbA1c. The sample will

be analysed instantly, and the result will be available in the patient's EMR *Sundhedsplatformen* within 5-10 min for the investigator /study personnel to assess.

The screening also includes a personal interview with the patient according to a study specific standard operational procedure (SOP) to assess the patient's type of diabetes, place of standard care, age, diabetes duration, glucose lowering regime , use of continuous glucose monitoring (CGM), previous participation in a BCC course, existing carbohydrate counting practices including use of a bolus calculator, gastroparesis, daily intake of carbohydrates, current pregnancy or plans of pregnancy, breastfeeding, uncontrolled medical issues or concomitant participation in other clinical studies and language skills in Danish.

If a participant is not eligible for inclusion in the study the cause of screening failure will be recorded, and the patient will be offered participation in the BCC course as a patient instead of as a study participant.

9.8 Randomisation

Participants eligible for inclusion in the study according to the screening will have the baseline measurements collected followed by a randomization carried out by the study investigator/study personnel.

A total of 226 participants will be randomly allocated in a 1:1 ratio to one of the following groups:

- 1) BCC
- 2) Control

Randomization will be performed by the investigator at visit 1 (V1) after the baseline examination. Participants will be randomly assigned to one of two groups with a 1:1 allocation by use of a computer-generated randomization schedule using the software system REDCap. The randomization list will be generated and kept securely by the clinical responsible investigator. The randomization is done by stratifying the participants based sex, BMI and HbA1c at baseline. The randomization is done in blocks to ensure an equal number of participants in each group.

9.9 Patient outcome

Expected patient outcomes are improved glycaemic control. All participants will be offered their personal study test results after they have completed the study period.

9.10 Study feasibility

SDCC has the facilities to carry out the study. SDCC has a kitchen for patient education called "FoodLab" designed to carry out group education programs with hands-on activities to practice food and self-management skills related to diabetes e.g. courses in BCC.

Approximately 6,000 patients with T2D are treated at SDCC and SDCC-Gentofte Hospital and only a limited number of these patients have already attended an education program in BCC at SDCC. At least 15 courses in BCC are needed for education of 113 patients in the BCC group based on the assumption that we can recruit eight patients with T2D for each course not taking into account potential relatives and patients participating. During the last four years, 64 patients with T2D have

attended the BCC program at SDCC. We will implement approximately 8 courses per year from 2018 equal to 64 patients per year.

One or two new courses in the BCC program will be initiated every third week at SDCC for patients with T2D except for holiday periods. Patients who do not wish to participate in the study or who do not fulfil the inclusion criteria will be included in the BCC courses together with BCC study participants. Additionally, some relatives will also be offered the opportunity to attend the BCC courses, if patients need extra support to manage dietary changes based on an individual assessment by the principle study investigator.

10 Examinations

All patients found eligible for inclusion in the study will be invited to a first study visit (V1) for collection of baseline measurements up to four weeks before the intervention according to study specific SOPs. Subsequently, all participants will be randomized to one of the two study groups. All examinations will be performed in the outpatient diabetes clinic at SDCC. Study visits and examinations are described in detail in **table 1** below and in the current section and section 11.

Visit no Time, week no from start of intervention	Contact -8 to -4	Scree ning	V1 -4 to -1	V2 0-2	V3 4-12	V4 14-20	V5 24	V6 48	Described in section
Participant-related information									
Study information	Х								9.6
Informed written consent		Х							9.7
Eligible for inclusion		Х							9.7
Randomisation		Х							9.8
Efficacy outcomes									•
HbA1c		Х	Х	Х	Х	Х	Х	Х	10.2
Plasma lipids			Х				Х	Х	10.2
Body weight			Х	Х	Х	Х	Х	Х	10.1
Height			Х						10.1
Blood pressure			Х				Х	Х	10.1
Waist and hip circumference			Х				Х	Х	10.1
Blood samples, fasting			Х				Х	Х	10.2
Blood samples, non-fasting		Х		Х	Х	Х			10.2
Urine samples			Х				Х		10.3
CGM including PG for 6 days			Х				Х		10.4
DXA			Х				Х		10.5
Questionnaires & Forms									•
F: 4-days dietary registration			Х				Х		10.6
Q: Carbohydrate estimation accuracy			Х				Х	Х	10.7
Q: Mathematical literacy			Х				Х	Х	10.7
Q: Diet-related quality of life			Х				Х	Х	10.7
Q: Perceived Competencies in Diabetes Scale			Х				Х	Х	10.7
Q: Health-Care Climate			Х				Х		10.7
Q: Treatment satisfaction			Х				Х	Х	10.7
Q: Demographic data			Х						10.9
Q: Physical activity			Х				Х	Х	10.10
Intervention									
Standard dietary counselling				Х	Х	Х			9.3.1
BCC*				X	X	x			932

Table 1: Schematic overview of study visits

Abbreviations CGM=continuous glucose monitoring d=day; DXA=Dual-energy-X-ray absorptiometry; F=forms; no=number; PG=plasma glucose; Q=Questionnaire; V=visit.

*BCC group only

10.1 Clinical examination

Body weight will be measured at all study visits. Measurements at visits V1 (baseline), V5 (week 24) and V6 (week 48) will be in a fasting condition and measurements at V2, V3 and V4 in a non-fasting condition. Height will only be measured and recorded at V1. Blood pressure, waist and hip circumference will be performed at visits V1, V5 and V6. Procedures will be conducted after appropriated training of study personnel involved in carrying out the procedures.

Body weight will be measured with the participant wearing light indoor clothes and no shoes at the same calibrated scale at all visits after emptying the bladder. Two measurements are done, and both are noted to the nearest 0.1 kg. The average of the two measurements is used in further analysis.

Height is measured using a wall-mounted stadiometer with the participants not wearing shoes and with the heels, buttocks and upper part of the back remaining in contact with the wall/back of the stadiometer. Two measurements are made and both results are noted to the nearest 0.1 cm. The average of the two measurements is used in further analysis.

Waist circumference is measured halfway between the lowest point of the costal margin and highest point of the iliac crest at the end of expiration with the participant in a standing position. All anthropometric measurements are performed twice with the average of the two measurements used in further analysis.

Hip circumference is measured at the level of the greater femoral trochanter; both are measured to the nearest 0.5 cm at the end of expiration with the participant in a standing position. All anthropometric measurements are performed twice with the average of the two measurements used in further analysis.

Blood pressure is measured with the participant in sitting position after minimum 10 min of rest, not talking during the measurement. Blood pressure measurements are repeated three times separated by two min breaks. Mean values are calculated.

10.2 Blood samples

Participants must attend V1, V5 and V6 after 8-10 hours of fasting having consumed only water for collection of blood samples. A small venous catheter will be inserted in one of the participant's arms for blood sampling which will be performed by a trained biomedical laboratory technician in the Clinical Biochemical Department at SDCC. The samples will be used for assessment of C-peptide, triglycerides, total cholesterol, HDL-C, LDL-C, very-low-density-lipoprotein cholesterol (VLDL-C), HbA1c, fasting glucose, haemoglobin, creatinine, albumin, potassium, sodium, alanine aminotransferase (ALAT), thyroid-stimulating hormone (TSH), leucocytes, thrombocytes, cobalamin and alkaline phosphatase according to standard procedure. No tobacco smoking is allowed in the morning before the visit. HbA1c will also be measured at the screening visit and visits V2, V3 and V4 in a non-fasting condition.

10.3 Urine samples

At V1 and V5 the participants will be provided with oral and written instructions on how to collect urine samples as midstream urine spots four times daily (preferably in the morning, afternoon and evening) for four days (three of which are the same days as the participants record their dietary food intake, while wearing a CGM). Participants are asked to hand in the urine collection at V2 for baseline measurements and by mail or in person after V5. Urine samples are analysed for content of albumin and creatinine as well as excretion of biomarkers related to carbohydrate intake (sucrose,

fructose, mannose and lactose) and qualitative markers of common groups of carbohydrate rich foods including vegetables, fruit, whole grain, and possibly potato, beet root, and rice. Participants are asked to hand in their urine samples in person to the laboratory at SDCC no later than one week after the urine collection.

10.4 Continuous Glucose Monitoring

The iPro[®]2 CGM system will be used. The CGM will be inserted under the skin on the lower part of the abdomen (under the umbilicus) by the investigator or study personnel at V1 and V5 for use in a period of six days. Participants will receive a glucometer together with oral and written instructions about how to measure glucose levels four times a day while wearing the CGM. Measurements are to be taken before breakfast, before lunch, before main evening meal and before bedtime. Participants are asked to hand in the CGM at V2 after baseline measurements and by mail or in person after six days of use after V5.

10.5 Body fat distribution

A DXA scan will be performed at V1 and V5 to measure body composition. A pregnancy test will be performed in all fertile women at V1 according to national requirements and procedures for X-ray equipment. At V5 a urine pregnancy test will be performed if a menstrual period is missed or if pregnancy is suspected. If the test is positive, the scan will not be conducted and the participation in the study is stopped immediately. The DXA scan will be performed in a fasting state with the participants only wearing light clothing and after emptying the bladder. The participant will lie still on a table while a machine arm passes over their entire body, which emits a high- and a low-energy X-ray beam. By measuring the absorption of each beam into parts of the body, readings for bone mineral density, lean body mass and fat mass will be obtained. The same device and software will be used for all participants throughout the study and must be calibrated according to manufacturer's instructions. The DXA scan will be conducted by the investigator or study personnel that have completed the mandatory course for non-medical staff operating DXA.

10.6 Dietary assessment

Participants are asked to complete four days of weighed dietary food records after V1 and V5. Participants will receive oral and written instructions about how to record their food intake in the same four days as they collect their urine and while wearing a CGM, preferably on four consecutive days including three weekdays and one day in the weekend to capture a representative weekly diet for assessment of total energy and macronutrient intake. All food and beverages consumed during the three days of recording must be noted in a dietary registration form with as many details as possible which include recording of pre- and post-meal plasma glucose levels, physical activities and for insulin users - insulin type and dose taken are also recorded (appendix 6). The exact amount of the food should be determined preferably by weighing the food on a digital scale, but in situations where this is not possible (e.g. when dining out) the estimated portion size using household measurements or other well-defined units will be accepted. Participants are asked to hand in the dietary registration form at V2 for baseline measurements and by mail or in person after V5. Instructions will be giving by study personal with a nutritional background well trained in performing and assessing dietary food records. After receiving the dietary registration forms the records will be visually inspected immediately for clarification of possible misunderstandings. Subsequently, the nutrient intake based on the dietary records will be calculated using the software system Vitakost (Vitakost Aps, Kolding) where nutrient and energy calculations are based on the Danish national food database. The dietary food records are used to estimate total energy intake (kJ/d), total carbohydrate intake (g/day and g/meal) and total dietary fibre intake (g/d g/10 MJ).

10.7 Questionnaires

Questionnaires on diabetes diet-related quality of life questionnaire (DDRQOL) (appendix 7), Perceived Competencies in Diabetes Scale (PCS) (appendix 8), Health-Care Climate Questionnaire (HCCQ) (appendix 9), accuracy in carbohydrate portion size estimation assessed by a carbohydrate photographic questionnaire (CPQ) (appendix 10), mathematical literacy based on a mathematical literacy test (appendix 11), and level of physical activity as assessed by International Physical Activity Questionnaire Short Form (IPAQ SF) (appendix 12) will be send out electronically through the software system REDCap before visits V1, V5 and V6. Participants preferring to fill in the questionnaires at the study site will be offered access to a tablet or laptop at SDCC and support by study personnel as needed.

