9.3 Interventions

9.3.1 Basic carbohydrate counting intervention

Participants randomized to the BCC intervention group will receive standard dietary care targeted patients with T2D treated in a specialized outpatient diabetes clinic with a BCC program as an addon. The routine dietary care includes one initial individual dietary counselling (60 min) and two individual follow-up counselling sessions (2 x 30 min) by a trained dietitian. The BCC program is described below.

Composition of the BCC program:

- Two 180 min interactive group sessions
- One 120 min interactive follow-up session

The BCC program consists of two sessions of three hours with two weeks in between and a follow-up session of two hours after 10 weeks delivered by trained dietitians. The BCC program is a group-based educational program based on several years of experience with this BCC concept at SDCC. The BCC program uses trained dietitians as educators following a planned curriculum which include experience-based leaning with problem-solving exercises, hands-on activities, short theoretical presentations, discussions of motivational aspects and coping strategies. The BCC program integrates peer modelling, skill development, goal setting, observational learning and social support into the program content and activities. The training includes identifying carbohydrates in food, reading carbohydrate tables, calculating the carbohydrate content from food labels, tables and applications (app) for smartphones and use of a personalized carbohydrate plan with guiding suggestions for daily

intake of carbohydrates at meals based on personal dietary recordings including plasma glucose measurements. An app from the Danish Diabetes Association (*Diabetes og Kulhydrattælling*[®]. The Danish Diabetes Association's app, Pragma soft A/S, available in Google Play[®] and App Store[®] 12/2014, Free) will be introduced to support estimation and calculation of carbohydrates.

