11.3 V1: Baseline (week -4 to -1)

At visit 1 the following procedures and assessments will be performed in the morning after 8-10 hours fast:

- Collection of fasting blood samples
- Measurement of height, body weight, blood pressure, hip and waist circumference (fasting)
- Pregnancy test (woman only)
- Full body DXA scan (fasting condition)
- A meal is provided for the participant
- Fill in questionnaire concerning demographic data, CPQ, Mathematical literacy test, DDRQOL, PCS, HCCQ, IPAQ SF at V1
- Collection of medical history including registration of glucose- and lipid-lowering medicine
- Instruction in how to fill out the three days of dietary registration forms
- Instruction in how to collect four days of urine sample and how to hand in the sample
- Injection of CGM device and instruction in precautions and how to hand in the CGM
- Instruction in recording four daily PG measurements in six days with CGM

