11.7 V5: After 24 weeks of intervention

At visit 5 the following procedures will be performed in the morning after 8-10 hours fasting:

- Collection of fasting blood samples
- Measurement of body weight, blood pressure, hip and waist circumference (fasting condition)
- Check for pregnancy (women only)
- Full body DXA scan (fasting condition)
- A meal is provided for the participant
- Participants who has not filled in all questionnaires before V5 will be asked to fill in at V5
- Update of glucose- and lipid-lowering medicine
- Instruction in how to fill out the three days of dietary registration forms
- Instruction in how to collect four days of urine sample and how to hand in the sample
- Injection of CGM device and instruction in precautions and how to hand in the CGM
- Instruction in recording four daily PG measurements in six days with CGM

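### The photographic carbohydrate-estimation test can be completed off site with no stated closed-book rule, while only the BCC arm is trained on tables, labels and an app, so its between-arm difference could partly reflect look-up.

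*Protocol*

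**What the plan says.** Protocol section 10.7 lists the CPQ (appendix 10) and the mathematical literacy test (appendix 11) alongside the quality-of-life, perceived-competence, health-care-climate and physical-activity questionnaires. All of these "will be send out electronically through the software system REDCap before visits V1, V5 and V6". Completion at the centre is optional: "Participants preferring to fill in the questionnaires at the study site will be offered access to a tablet or laptop at SDCC", with help from personnel if needed. Section 11.7 makes the visit itself the fallback: "Participants who has not filled in all questionnaires before V5 will be asked to fill in at V5". Section 11.8 has the same rule for V6.

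Section 9.3.1 describes the BCC curriculum. It includes reading carbohydrate tables and "calculating the carbohydrate content from food labels, tables and applications (app) for smartphones". It also names a free app that "will be introduced to support estimation and calculation of carbohydrates". Section 9.3.2, on the control arm, mentions none of these tools, although counselling there may touch on carbohydrate sources.

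Protocol section 9.1.2 makes carbohydrate estimation accuracy a secondary outcome, compared between groups at weeks 24 and 48. SAP section 6 scores it as percentage estimation error on 11 high-carbohydrate foods, counting only foods the participant reports eating. The treatment effect is a baseline-corrected difference between groups at the SAP's V2 and V3, which are the protocol's V5 and V6.

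**The concern.** A self-report scale has no correct answers to look up. An accuracy test does, and its result depends on what the participant has to hand. Away from the clinic, a participant may consult an app, a table, a food label or a relative. If that happens equally in both arms, the contrast between arms is largely protected. Here the trial itself teaches one arm to use these tools and does not teach the other. Section 9.3.1 also admits close relatives to the BCC courses where extra support is needed, so a helper at home may have been trained too, again only in the BCC arm.

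What is at stake is the meaning of one secondary outcome. A smaller estimation error in the BCC arm would naturally be reported as better estimation skill. Protocol section 7.1 names estimation accuracy as one route by which BCC might act on clinical outcomes, so the reading of that sub-hypothesis would be affected as well.

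**Working it through.** The plan states no figure on this point, so the check compares the relevant provisions and then follows the planned estimator.

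1. **Conditions of the test.** Sections 10.7, 11.7 and 11.8 together allow the CPQ to be finished before the visit, away from staff. Neither supplied document states a supervision rule, a time limit or a ban on aids, and neither plans to record where the test was taken or what was used.

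2. **Difference between arms.** Tables, labels and the app are in section 9.3.1 (BCC) and absent from section 9.3.2 (control). The SAP describes the trial as open-label.

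3. **Timing.** V1 falls in weeks -4 to -1 (section 11.3). The first BCC session is placed at week 2 (section 11.4.1). The training therefore comes between the baseline CPQ and the two later ones.

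4. **What the estimator does with this.** At a visit after baseline, let pB and pC be the shares of BCC and control participants who use an aid, and let dB and dC be the mean reduction in percentage error among those users. If unaided skill does not differ between the arms, then

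   expected difference in mean error (BCC minus control) = -(pB x dB - pC x dC).

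   Before training, randomisation gives no reason for the two products to differ, so the expected baseline difference is about 0. Baseline correction then removes about 0 and leaves the whole post-baseline term in place. The repeated measures model in SAP section 6 therefore cannot correct for look-up that starts after V1.

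5. **Direction and bounds.** If pB x dB exceeds pC x dC, the bias favours BCC. Its absolute size then runs from just above 0 (products nearly equal) up to dB (every BCC participant looks up and no control does). None of the four quantities is in the documents, so the size cannot be narrowed further.

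6. **Other safeguards in the SAP.** The false discovery rate correction for secondary outcomes deals with chance findings across many tests. It does not remove a systematic difference in test conditions. No analysis by completion setting is planned; additional analyses are declared not relevant.

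**The case against.** Several counter-arguments carry weight.

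- **Unseen instructions.** A closed-book instruction could be in appendix 10 or in a study-specific procedure, neither of which is supplied. This stands as a limit. An instruction alone would still be unenforced off site, and the protocol body should cite it.
- **Aided estimation is taught.** Using tables and apps is part of BCC, so aided performance could be a legitimate target. Neither document says whether aided or unaided estimation is measured. That argues for defining the target, and it does not make the present result interpretable as unaided skill.
- **Look-up may help little.** If the portion has to be judged from a photograph, a table entry does not supply the whole answer. The app is also free and public, so controls could use it. Both points reduce the possible bias; neither excludes it.

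A reader might also infer three stronger things that the documents do not support.

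- **That the mathematical literacy test has the same arm-specific problem.** Its content is not supplied, a carbohydrate table does not plainly answer a numeracy item, and calculators are open to both arms.
- **That the setting changes from clinic at baseline to home later,** because section 11.3 has "Fill in questionnaire concerning demographic data, CPQ, Mathematical literacy test, DDRQOL, PCS, HCCQ, IPAQ SF at V1". That line reads as a visit checklist: it also covers demographics and IPAQ SF, which sections 10.9 and 10.10 send out before V1. A change of setting common to both arms would not by itself bias the contrast.
- **That a false-positive rate can be attached to this.** Any such rate would rest wholly on assumed look-up shares, gains and standard deviations.

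**Conclusion.** The point holds for the CPQ. As written, the plan allows off-site completion of an accuracy test whose look-up tools are taught to one arm only, after baseline. A difference in estimation error at weeks 24 and 48 could partly reflect look-up, and the planned baseline correction cannot take it out.

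The size is unknown, and actual look-up is not shown. The conclusion assumes that appendix 10 and the study procedures contain no effective closed-book rule, and that look-up would be more frequent or more useful in the BCC arm.

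The reach is limited. HbA1c is a laboratory measure and MAGE comes from the glucose sensor, so the primary outcomes are unaffected. A reader might infer that a mediated HbA1c effect would be wrongly claimed, but neither document specifies a mediation model. The consequence is confined to interpreting this secondary outcome and the related sub-hypothesis.

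**What to change.** **Protocol.** State that the CPQ measures unaided estimation. Take it out of the pre-visit REDCap mailing, and have both arms complete it on the study tablet or laptop at V1, V5 and V6, without app, tables or helper. Use the same wording in sections 10.7, 11.3, 11.7 and 11.8. If appendix 10 already has such a rule, cite it there. The self-report scales can stay as they are. The mathematical literacy test may be moved too for uniform conditions, although arm-specific look-up is not shown for it.

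**Data already collected.** The SAP describes trial conduct in the past tense, so this part may matter most. Assuming REDCap completion times are available, report by arm and visit how many CPQs were completed before the visit and how many at it. This is an imperfect proxy for setting and says nothing about whether aids were used, so it should not be used to relabel the outcome as aided performance. State in the interpretation that aided completion cannot be excluded.

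**Cost.** A slightly longer V1, V5 and V6. Participants already attend these visits, and section 10.7 already offers the device and staff support. The retrospective step is one descriptive table and one sentence of interpretation.
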